#### 3. OBJECTIVE

The primary objective of this study is to determine and compare the efficacy and safety of HBP Foam and the VEH Foam applied twice daily for two weeks (Study Day 15 + 3 days) in subjects with plaque psoriasis.

#### 4. STUDY DESIGN

This is a Phase 3, double-blind, randomized, multicenter, vehicle-controlled, parallel group comparison study of HBP Foam and VEH Foam in adult subjects with plaque psoriasis. Approximately 400 subjects (200 per treatment group) with stable plaque psoriasis involving a minimum of 2% and no more than 12% BSA (excluding the face, scalp, groin, axillae and other intertriginous areas) who fulfill the inclusion/exclusion criteria will be enrolled at approximately 20 U.S. study sites. Subjects will be randomized in a 1:1 ratio to one of two treatment groups:

- 1. Halobetasol Propionate Foam, 0.05% (HBP Foam)
- 2. Halobetasol Propionate Foam Vehicle (VEH Foam)

All subjects will apply the assigned test article to all psoriasis plaques twice daily for 14 (+3) days.

### 5. STUDY POPULATION

The "Treatment Area" is defined as all areas of the body (excluding the face, scalp, groin, axillae, and other intertriginous areas).

To qualify for this study, per inclusion criterion #4, the subject must have a clinical diagnosis of stable plaque psoriasis involving 2 to 12% total body surface area (BSA) within the Treatment Area. See Section 10.4 for BSA calculation.

### 5.1 Subject Eligibility

To be included in the study, subjects must meet the following inclusion and none of the exclusion criteria.

### 5.1.1 Inclusion Criteria

- 1. Subject is male or non-pregnant female and is at least 18 years of age at the time of the Screening Visit.
- 2. Subject has provided written informed consent.
- 3. Subject is willing and able to apply the test article(s) as directed, comply with study instructions and commit to all follow-up visits for the duration of the study.
- 4. Subject has a clinical diagnosis of stable plaque psoriasis involving body surface area (BSA) (excluding the face, scalp, groin, axillae and other intertriginous areas).
- 5. Subject has an Investigator's Global Assessment (IGA) score of at least three (3 = moderate) at the Baseline Visit.
- 6. Females must be post-menopausal, surgically sterile or use an effective method of birth control with a negative urine pregnancy test (UPT) at the Baseline Visit.

### 5.1.2 Exclusion Criteria

- 1. Subject has spontaneously improving or rapidly deteriorating plaque psoriasis.
- 2. Subject has guttate, pustular, erythrodermic, or other non-plaque forms of psoriasis.

<sup>7 1% BSA is approximately equal to the surface area of the subject's palm and fingers, with the fingers extended yet grouped together, creating a flat oval-like surface area. For BSA determination residual discoloration (pigmentation and/or erythema) should not be included.

<sup>8 Defined as amenorrhea greater than 12 consecutive months in 55 years of age and older.

<sup>9 Hysterectomy, bilateral tubal ligation (at least six months prior to initiation of treatment) or bilateral oophorectomy.

Effective forms of birth control include hormonal contraceptives [oral, injectable, transdermal, or intravaginal] or intrauterine device (IUD) for two cycles (e.g., 8 weeks) (note: for Depo-Provera the requirement is at least 7 days after injection) prior to test article application, condom and spermicidal, or diaphragm and spermicidal. Other acceptable forms of birth control include: a) abstinence for subjects who are not sexually active or b) if the subject is in a monogamous relationship with a partner who is sterile (e.g., vasectomy performed at least six months prior to the subject's initiation of treatment). Subjects who become sexually active or begin to have relations with a partner who is not sterile during the trial must agree to use an effective form of birth control for the duration of the study.

Women of childbearing potential (WOCBP) taking hormonal therapy must be on treatment for two cycles (e.g., 8 weeks) prior to study entry.

<sup>12 UPTs must have a minimum sensitivity of 25 mIU β-hCG/mL.

- 3. Subject has a physical condition which, in the investigator's opinion, might impair evaluation of plaque psoriasis, or which exposes the subject to an unacceptable risk by study participation.
- 4. Subject has used any phototherapy (including laser), photo-chemotherapy, or other forms of photo based therapy for the treatment of their psoriasis within 30 days prior to the Baseline Visit.
- 5. Subject has used any systemic methotrexate, retinoids, systemic corticosteroids [including intralesional, intra-articular, and intramuscular corticosteroids], cyclosporine or analogous products within 90 days prior to the Baseline Visit.
- 6. Subject has used any systemic biologic therapy (i.e., FDA-approved or experimental therapy) within five (5) half-lives of the biologic prior to the Baseline Visit. Published or documented half-life of the product provided by the commercial supplier or Sponsor should be used to establish this value.
- 7. Subject had prolonged exposure to natural or artificial sources of ultraviolet radiation within 30 days prior to the Baseline Visit or is intending to have such exposure during the study which in the opinion of the investigator is thought to modify the subject's disease.
- 8. Subject has used topical body (excluding the scalp) psoriasis therapy (including coal tar, anthralin, steroids, retinoids, and vitamin D analogs) within 14 days prior to the Baseline Visit.
- 9. Subject has used emollients/moisturizers on areas to be treated within four hours prior to clinical evaluation at the Baseline Visit.
- 10. Subject is currently using lithium or Plaquenil (hydroxychloroquine).
- 11. Subject is currently using a beta-blocking medication (e.g., propranolol) or angiotensin converting enzyme (ACE) inhibitor at a dose that has not been stabilized, in the opinion of the investigator.
- 12. Subject has a history of sensitivity to corticosteroids or any of the ingredients in the test articles (see Section 6.1).
- 13. Subject is pregnant, lactating, or is planning to become pregnant during the study.
- 14. Subject is currently enrolled in an investigational drug or device study.
- 15. Subject has used an investigational drug or investigational device treatment within 30 days prior to the Baseline Visit.
- 16. Subject has been previously enrolled in this study and treated with a test article.
- 17. Subject is known to be noncompliant or is unlikely to comply with the requirements of the study protocol (e.g., due to alcoholism, drug dependency, mental incapacity) in the opinion of the investigator.

#### 5.1.3 Subject Withdrawal Criteria

Procedures for handling subjects who are discontinued from the study are described in Section 13.2. Subjects who are discontinued will not be replaced.

### 6. TEST ARTICLES AND REGIMEN

### 6.1 Description

Test article #1:

Active ingredient:
Other ingredients:

Halobetasol propionate

Halobetasol propionate

Halobetasol Propionate

Halobetasol Propionate Foam Vehicle (VEH Foam)

# 6.2 Instructions for Use and Application

Subjects will apply the assigned test article (HBP Foam or VEH Foam) to all psoriatic plaques in the Treatment Area twice daily for two weeks.

Subjects will be provided with an instruction sheet (refer to Appendix 1) which includes detailed instructions for the application of test article.

The Treatment Area must be a minimum of 2% and no more than 12% BSA to fulfill study inclusion requirements.

### 6.2.1 Test Article Application

At the Baseline Visit, a study staff member will demonstrate how to dispense the test article and instruct the subject on the proper application of the test article to the Treatment Area (as defined in Section 5).

Subjects should be instructed to wash their hands before and after each test article application. Instructions are as follows:

Subjects should apply a thin uniform film of the assigned test article twice daily (morning and night) to all psoriatic plaques in the Treatment Area for two weeks (Study Day 15 + 3 days). The subject should ideally allow approximately eight hours or more separation between dose applications; not wash the treated area for at least four hours following test

article application, and should not apply the test article within four hours prior to any study visit. Areas that should NOT be treated under any circumstances include any areas of active psoriasis on the face, scalp, groin, axillae, or other intertriginous areas. Occlusion of treated areas is prohibited.

At each follow-up visit during the study, the investigator or designee should review proper application of the test article to all lesions designated for treatment.

As the subject's psoriatic plaques improve or worsen, the amount of test article applied will likely decrease or increase, respectively. Subjects with extensive disease which would typically require more than 50 grams of test article per week should not be enrolled in this study. If the subject's disease becomes unmanageable because of these limitations, they should be discontinued from the study as treatment failures.

The standard bland emollient provided for study use is ONLY to be used by the subject to treat those anatomic locations that are excluded from treatment (i.e., face, scalp, groin, axillae, or other intertriginous areas). The emollient may be applied to these areas as frequently as the subject desires to treat his/her psoriasis. An investigator-approved medicated (non-steroid) shampoo can be used to treat scalp psoriasis.

#### 6.2.2 Treatment Duration

The subject will apply the test article to all psoriasis plaques twice daily for two weeks (Study Day 15 + 3 days).

#### 6.3 Warnings, Precautions and Contraindications

The test articles are for topical use only. Care should be taken to avoid contact with eyes and all mucous membranes. If contact with eyes occurs, rinse thoroughly with water. Do not apply to face, scalp, groin, axillae, or other intertriginous areas.

Subjects with a known sensitivity to any of the ingredients in the test articles should not participate in this study.

Should skin irritation or rash develop, discontinue use.

Subjects should not occlude the treated areas.

In case of accidental ingestion, subjects should contact the investigator immediately.

The effects of halobetasol propionate in nursing mothers, pregnant women, and their unborn children are unknown. WOCBP must not be pregnant or planning a pregnancy during the study period.

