### 7. RANDOMIZATION ASSIGNMENT

[figure not shown]
Subjects who are eligible for enrollment into the study will be randomized to receive HBP Foam or VEH Foam in a 1:1 ratio. The randomization scheme will be blocked by investigational site. At each site, subject kits (each containing three units) will be dispensed in ascending order as subjects are enrolled. At each site, the study staff will add the site number (provided to each site) and the subject number (starting with 001) to each kit label. The kit number dispensed to each subject will also be recorded on the source documents and CRFs. Treatment group designation will remain blinded until the final database is locked (unless unblinding is required as described in Section 15). Subject enrollment at the sites will be competitive. All subjects will apply the topical formulations as directed by the investigator.

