Test article is defined as a pharmaceutical form of an active ingredient (or "primary operational component" for devices) or vehicle/placebo being tested or used as a reference in the study, whether blinded or unblinded. AEs may be either spontaneously reported or elicited during questioning and examination of a subject. All AEs must be completely recorded on the AE CRF. If known, the investigator should report the diagnosis of the underlying illness or disorder, rather than its individual symptoms. Subjects experiencing AEs that cause interruption or discontinuation of test article, or those experiencing AEs that are present at the end of their participation in the study should receive follow-up as appropriate. If possible, report the outcome of any AE that caused permanent discontinuation or that was present at the end of the study particularly if the AE is considered by the investigator to be treatment-related (i.e., definitely, probably, or possibly related to test article).

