#### A 4.5 Dose Modifications

If any sign of test article intolerance occurs, the investigator may direct the subject to reduce the frequency of application by skipping a day or more of treatment. If irritation continues, or if the subject cannot return to twice-daily applications within approximately three days of reducing the application frequency, the subject should be removed from the study following the procedures in Section 13. Any medication intolerance should be recorded as an AE. The subject should not modify the treatment regimen without consultation with the investigator. All dose modifications must be reported on the Study Medication Compliance Form in the subject's CRFs.

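### Do the warning in 6.3 to discontinue use on skin irritation and the permission in A 4.5 to skip days conflict in a way that requires a change?

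*Combined protocol and SAP*

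**What the plan says.** Four places in the combined protocol and SAP bear on the point.

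- **Section 6.3 (Warnings, Precautions and Contraindications):** "Should skin irritation or rash develop, discontinue use". It sets no grade or duration, does not say whom it addresses, and does not say whether the stop is temporary or permanent.
- **Appendix A 4.5 (Dose Modifications):** the trigger is "If any sign of test article intolerance occurs". In that case "the investigator may direct the subject to reduce the frequency of application by skipping a day or more of treatment". Removal under Section 13 is called for in this case: "If irritation continues, or if the subject cannot return to twice-daily applications within approximately three days of reducing the application frequency". It adds: "The subject should not modify the treatment regimen without consultation with the investigator". Every modification goes on the Study Medication Compliance Form.
- **Section 7 (Randomization Assignment):** "All subjects will apply the topical formulations as directed by the investigator".
- **Section 14 (Adverse Event Reporting):** one sentence covers "Subjects experiencing AEs that cause interruption or discontinuation of test article", and another asks sites, where possible, to "report the outcome of any AE that caused permanent discontinuation".

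Section 6.3 does not refer to A 4.5. A 4.5 refers only to Section 13. Section 16.1 sends the reader to Appendix 4 for supply matters and does not list dose modification among them.

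**The concern.** A 4.5 speaks of irritation that continues, so it deals with subjects who already have irritation and are still in the study. Section 6.3 deals with the same event and reads as an unconditional stop. On a strict reading, a subject told to pause and then resume has not followed 6.3, and a subject who stops on the strength of 6.3 alone has not followed the consultation rule in A 4.5. A 4.5 does not name rash at all.

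Two sites could therefore manage the same mild reaction differently, and each could point to the protocol. Section 18.3 requires every deviation to be documented, and it is not obvious which conduct would be the deviation. The situation is foreseeable: Section 10.5 has burning/stinging, folliculitis and edema graded at every visit.

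**Working it through.** The point is textual. The documents give no rate of irritation, and the expected number of applications is not fixed for each subject: footnote 13 to Section 9.1 allows a single application on Day 1, and Section 13.1 allows 14 (+3) days. A dose count would therefore rest on assumptions alone, and none is offered. The check sets the passages side by side.

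1. **Same event?** For irritation, yes, from A 4.5's own wording. Rash is covered only if it is read as a sign of intolerance, which is a natural reading but not a stated one.

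2. **Can one course of action satisfy both sections?** Yes. A 4.5 gives the investigator an option and imposes no duty to use it. An investigator who stops treatment for irritation complies with 6.3 and leaves the A 4.5 option unused.

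3. **When do they collide?** Two conditions are needed together: the investigator uses the option, and the stop in 6.3 is permanent. The text does not establish the second. Section 14 speaks of interruption, of discontinuation, and separately of permanent discontinuation, so the bare verb in 6.3 need not mean a permanent stop.

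4. **Is there a reading that fits both?** The only reduction A 4.5 describes is skipping a day or more, which is itself a stop in use. Section 6.3 can be read as the immediate precaution and A 4.5 as what comes next: a pause, then either a return to twice-daily use or removal under Section 13. No sentence states this sequence, but no sentence excludes it.

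5. **Does the subject who stops alone break a rule?** That depends on whom 6.3 addresses. If it addresses the investigator, nothing conflicts. The document that subjects receive is the Subject Instruction Sheet in Appendix 1, and its content is not shown, so the scenario cannot be confirmed.

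6. **Is a directed pause a deviation?** Hardly. A 4.5 authorises it and requires it on a form. A 4.6 names it as an expected diary entry. Section 17.3.2 lists any change in dosing alongside each adverse event.

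7. **Is the analysis left undefined?** No.
   - The ITT population in 17.3 is set by randomization and dispensing, so a subject who pauses and a subject who stops are both in it.
   - Under 17.3.1.1 and 17.4, a subject who leaves before Day 15 for any reason, or has no Day 15 data, is a treatment failure. A subject who pauses and attends Day 15 is scored on the Day 15 IGA.
   - Compliance in 17.3.2 is descriptive, and the per-protocol analysis is supportive.

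**The case for a change.** The strongest case for acting is that 6.3 is an operative instruction, that nothing visible subordinates it to A 4.5, and that one clause with a cross-reference would settle the matter at almost no cost. It can be added that the choice matters for an individual: a subject withdrawn for irritation counts as a failure, whereas one who pauses and returns may be a success, and only the second is likely to stay in the per-protocol set.

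Much of this is right. The visible text does not say which section governs, whether the stop is permanent, or whether rash falls under A 4.5. The individual outcome can depend on how the reaction is managed.

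The step to a defect in the plan does not follow. Management would vary in any case, because A 4.5 leaves the reduction to the investigator and Section 13.2 permits withdrawal for adverse events. Section 15 requires those who make the clinical assessments to be blinded. No difference between arms caused by the wording has been shown, and the documents hold no figure from which to size one. Aligning the two sections would leave the endpoint, the populations and the missing-data rule as they are.

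**Conclusion.** No change to the plan is called for. Sections 6.3 and A 4.5 are not cross-referenced, and they conflict only if the stop in 6.3 is permanent and the A 4.5 option is used. This is missing detail that sites and analysts can handle sensibly: pauses are authorised and recorded, withdrawals have a stated outcome rule, and the primary analysis can be carried out as written. No effect on the results has been demonstrated, and none can be estimated without an irritation rate.

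The conclusion assumes that the Subject Instruction Sheet, which is not shown, does not itself give a contrary instruction. As ordinary editing, the sponsor's medical team should reconcile the two passages, say whether rash is included and whether the stop is temporary or permanent, and check that the sheet agrees. Which clinical rule should prevail is for that team, and no view is given here.

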### 7. RANDOMIZATION ASSIGNMENT

[figure not shown]
Subjects who are eligible for enrollment into the study will be randomized to receive HBP Foam or VEH Foam in a 1:1 ratio. The randomization scheme will be blocked by investigational site. At each site, subject kits (each containing three units) will be dispensed in ascending order as subjects are enrolled. At each site, the study staff will add the site number (provided to each site) and the subject number (starting with 001) to each kit label. The kit number dispensed to each subject will also be recorded on the source documents and CRFs. Treatment group designation will remain blinded until the final database is locked (unless unblinding is required as described in Section 15). Subject enrollment at the sites will be competitive. All subjects will apply the topical formulations as directed by the investigator.

#### 8. PRIOR AND CONCOMITANT THERAPIES

Current medications and any medications taken in the 30 days prior to the start of the study (Screening/Baseline, Visit 1) will be recorded as prior/concomitant medications (using their trade names, if known) with the corresponding indication. The medications to be recorded include prescription and over-the-counter (OTC) medications (except vitamins and dietary supplements). All medications taken on a regular basis should be recorded on this page prior to commencing the use of the test article.

Therapies (medication and non-medication therapies) not restricted by the protocol may be used during the study for the treatment or prevention of disease or to maintain good health. Vitamins and mineral supplements are permitted at dosages considered by the investigator as reasonable for maintaining good health. Non-prohibited chronic therapies being used at Visit 1 may be continued. Any changes in concomitant therapies during the study must be recorded on the Concomitant Therapy form. The reason for any change in concomitant therapies should be evaluated and, if appropriate, reported as, or in conjunction with, an adverse event.

# 9. STUDY PROCEDURES

Specific activities for each study visit are listed below.

### 9.1 Visit 1 (Day 1): Screening/Baseline

At this visit, the investigator or designee will:

- Obtain a signed, written informed consent unless the subject signed a consent within the past 45 days.
- Complete review and documentation of the subject's medical history and demographic information.
- Record any concomitant medications and therapies.
- Confirm subject meets I/E criteria.
- Have subject complete washout from any prohibited medications, if necessary.
- Perform baseline activities of Visit 1 which should occur within 45 days of screening activities. For those subjects that required a washout period related to

exclusionary medications, the investigator needs to reaffirm the subject meets all protocol requirements at Baseline.

- Perform a limited physical exam. The limited physical exam will include vital signs, height, weight, head and neck, pulmonary, cardiac and abdomen examinations, and an assessment of motor and gait function.
- Perform a UPT for all WOCBP; the results must be negative for the subject to be enrolled into the study.
- Identify the psoriatic plaques to receive treatment during the study. At this visit, the psoriatic plaques in the Treatment Area must include

  BSA to fulfill study inclusion requirements. Lesions on the face, scalp, groin, axillae, and other intertriginous areas will not be included in the percent BSA calculation.
- Record the location of the plaques to be treated with the test article in the CRFs.
- Document the percent BSA with active psoriasis in the Treatment Area (see Section 10.4).
- Perform Baseline clinical evaluations (IGA, clinical signs of psoriasis, and pruritus; see Section 10) prior to application of the test article.
- Record Baseline LSRs prior to application of the test article.
- Perform photography (selected study sites only; see Section 11).
- If the subject meets the I/E criteria, randomize the subject by assigning lowest available study medication kit number in ascending order. At each site, the study staff will add the site number (provided to each site) and the subject number (starting with 001) to each kit label. The kit number dispensed to each subject will also be recorded on the source documents and CRFs.
- Weigh and dispense initial canister(s) of test article.
- Complete the Study Medication Accountability Log.
- Dispense bland emollient provided, as required.

NOTE: The bland emollient is to be used only on non-diseased skin or diseased skin not being treated with the test article (i.e., the face, scalp, groin, axillae, and other intertriginous areas). Other emollients should be avoided during the trial except with the approval of the investigator to assure they are a bland emollient.

- Identify an investigator-approved, medicated (non-steroid) shampoo the subject will use for treating scalp psoriasis only, if appropriate.
- Dispense the Subject Instruction Sheet to the subject (Appendix 1). A body diagram may also be given to the subject to remind them where to apply (and where not to apply) the test articles. All psoriatic lesions in the Treatment Area must be treated with the test article.
- Dispense the Subject Diary (Appendix 2) to the subject and provide completion instructions.

• Have a study staff member instruct the subject where and how to apply the initial dose of test article following the procedures in Section 6.2.1. Subjects will apply the first dose of test article to all plaques under staff supervision in the clinic .

- Instruct the subject to continue twice daily applications of the test article as instructed to all psoriatic plaques in the Treatment Area identified at this visit AND any new psoriatic lesions in the Treatment Area that may occur subsequently.
- Record any AEs.
- Schedule Visit 2 (Day  $8 \pm 2$ ). Subjects should be instructed not to apply the test article within  $\frac{4 \text{ hours}}{2}$  prior to the scheduled clinic visit.

